CBIT success relies on an ability to suppress tics that many youth lack. The central aim of CBIT is to enhance voluntary tic suppression. Better tic suppression ability drives CBIT improvement¹⁰ and predicts lower tic burden over the course of illness.¹¹ During the core CBIT procedure, competing response training, patients learn to inhibit tics by engaging in a competing motor action. However, research shows that many youth lack this fundamental tic suppression ability that CBIT aspires to enhance. Tic suppression ability has been assessed in our laboratory and others using the Tic Suppression Task (TST), which quantifies tics using direct observation methods.¹² Data show minimal changes in tic frequency when youth are instructed to suppress tics (e.g., reduction from a mean tic frequency of 4 tics per minute during "free to tic" baseline to 3 tics per minute during attempted suppression¹³). Under the most ideal suppression context--in which immediate reward is given for successful suppression--only 20% of youth

PROTOCOL TITLE: Transcranial Magnetic Stimulation to Augment Behavior Therapy for Tics VERSION DATE: 2/24/2022

can suppress tics to near-zero levels, and another 20% show no detectable tic decrease or even tic worsening when attempting suppression.¹² Enhancing tic suppression ability is likely to enhance the efficacy of CBIT.

2.2. Preliminary Data: Our preliminary data show that tic suppression ability can be enhanced with inhibitory, noninvasive stimulation of supplementary motor area (SMA), an approach built upon established knowledge of tic neurocircuitry. Tics result from dysfunctional activity in cortico-striatal-thalamo-cortical circuits (CSTC).^{14,15}

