- Tic Suppression Task (TST) procedures: The TST will be our primary measure of behavioral target engagement. In this paradigm, a participant is seated alone in a room in front of a computer capturing a video recording of tic occurrences for later coding by independent raters. TST will consist of two 3-min conditions: 1) free-to-tic (FT): youth is instructed to stay seated and tic freely, a measure of naturally occurring tic frequency (tics per minute) ; 2) suppression: youth is instructed to suppress tics. Videos will be coded to establish tic frequencies using a computerized behavioral coding program.
- Neuroimaging procedures. MRI and fMRI data acquisition: A Siemens Prisma 3T scanner located at the Center for Magnetic Resonance Research (CMRR) will be used for image acquisition. To minimize motion artifact, we will immobilize the participant's head with foam wedges that fit snugly between the head and 32channel receive only head coil. As needed, we will re-run scans or bring back participants for a repeat scan session. We will acquire the following data: 3D T1 ME-MPRAGE, 3D T2 SPACE, resting fMRI, spin Echo fMRI reverse phase encode scan pair, finger tapping task. The Finger Tapping Task will be used for functional localization of SMA. This task is used to isolate neural activity in

PROTOCOL TITLE: Transcranial Magnetic Stimulation to Augment Behavior Therapy for Tics VERSION DATE: 2/24/2022

motor planning and execution areas, including SMA, and is a highly reliable, well-established fMRI task used for motor mapping⁵³ and for TMS targeting of motor cortex and SMA by our group and others.³³ A whole-brain activation map showing the contrast of rest vs. active tapping will be created for each person to determine the precise placement of the TMS coil.

- **Randomization:** Randomization will occur after pre-treatment assessments. Randomization will be stratified on baseline TST performance (tic suppressibility below or above 50%) and medication status (on vs. off).
- Intervention Protocol: CBIT+TMS. TMS will be delivered immediately prior to the start of CBIT sessions (see figure 2).
- **CBIT Protocol** will follow the published CBIT manual⁵⁴ tested in the large trials that established CBIT efficacy in children and adults.^{8,9} Participants will receive 10 sessions of CBIT, 1 session per

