- **Premature Termination.** At any time, participants may deteriorate or develop clinical exigencies that lead study staff to recommend additional out-of-protocol treatments above and beyond that provided by ASAP guidelines (e.g., change in medications during the study). Such participants will be considered "premature terminators" (PMT) and classified as a protocol violation. In order to enhance the ITT analyses, "prematurely terminated" participants will continue to be treated within their assigned treatment arms insofar as possible, and assessments will continue according to protocol.
- Analysis population will be an intent-to-treat population including all enrolled participants who completed at least 1 CBIT session.
- Treatment of Missing Data: All participants will remain

PROTOCOL TITLE: Transcranial Magnetic Stimulation to Augment Behavior Therapy for Tics VERSION DATE: 2/24/2022

in the study unless consent is withdrawn or there are concerns about patient safety. While there is little that can be done to address missing data when participants drop out during the training process itself, we can compare baseline characteristics of those who drop out at this time versus those who do not and adjust models based on significant predictors of dropout. For those who drop out during the follow-up period or miss some assessments during followup, we will use multiple imputation by chained equations (MICE) to allow for missing data without loss of those cases from the model under the assumption of Missing at Random (MAR). Sensitivity Analysis: If dropout status appears to be Missing Not At Random (MNAR), i.e., dropout is associated with an unobserved outcome, we will run sensitivity analyses using MICE to compare imputed and non-imputed models results to assess robustness of statistical inference.

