• Aim 1. Target engagement: Brain. 1) Primary measure of neural target engagement will be decreased activation in SMA. Hypothesis 1: Either or both active TMS groups will demonstrate within-subject decrease (effect size $\eta 2=0.18$ in an ANOVA) in SMA activation post-treatment, as measured with an fMRI finger tapping task. While this is a large effect size in practice, we point out that Wu et al (2014) observed a much larger effect size of η 2=0.41 in the decrease in SMA activity comparing active vs sham cTBS. 2) Secondary measure of neural target engagement will be change in fMRI resting state functional connectivity of at least one SMA-mediated circuit (SMA-DLS, SMA-M1). Hypothesis 2: Either or both active TMS groups will demonstrate within-subject change (effect size $\eta 2=0.18$ in an ANOVA) in resting state fMRI connectivity (RSFC) of at least one SMA-mediated circuit (SMA-DLS, SMA-M1) post-treatment. A region of interest (ROI) analysis will be performed to determine the time*treatment group differences in SMA activation elicited by an fMRI motor task (finger tapping). The SMA ROI will be identified by placing a seed (sphere with 5mm radius) that matches the coordinate used for individual TMS coil placement. Activation parameters in the SMA will be identified in a first-level analysis, using a general linear model (GLM) to model each subject's SMA time course during the motor task. These activation parameters will be used in a subsequent linear mixed effects (LME) model. The predictors of the LME will include the baseline activation, group indicators for

PROTOCOL TITLE: Transcranial Magnetic Stimulation to Augment Behavior Therapy for Tics VERSION DATE: 2/24/2022

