the stimulation groups, and baseline x group interactions. Random effects will be used to model within-subject variation from the first-level analyses. Altogether, the LME will allow us to model how the within-subject change in activation from pre-treatment to post-treatment differs across active and sham conditions. *In addition*, we will also investigate the effects of each TMS regimen on the connectivity in the entire CSTC. To this end, we will extract the ROI-level time courses from each region in the CSTC, and we will use partial correlations to obtain an estimate of connectivity between each ROI pair within the CSTC while accounting for the data observed in the other ROIs. Given the collection of partial correlations for each study participant, we will use the SPU test, which uses the collection of partial correlations simultaneously, to assess for group differences across the sham and TMS regimens.⁷⁵

- Aim 2. Target engagement: Behavior. Hypothesis: Either or both active TMS groups will show within-subject improvement (small effect size of at least Cohen's d = 0.3) in tic suppression ability as measured by the Tic Suppression Task (TST). TST "tic suppression ability" scores will serve as the primary outcome in an ANOVA model. An ANOVA will be used to establish if there exist differences in how the 1Hz, cTBS, and sham conditions affect change in tic suppression ability from pre- to post-treatment. Group indicators for these conditions will be the primary predictors for the model.
- Aim 3. Assess dose-response relationship. Changes in brain (Aim 1) and behavior (Aim 2) targets will be compared between active TMS groups (1Hz rTMS vs. cTBS) using ANOVA. In the case that both active TMS regimens are found superior to sham, we will compare the regimens on safety and feasibility. We will use 2-sample t-tests to compare the two regimens using data from our safety and feasibility measures and prioritize the regimen with significantly better (p<.05) outcomes.
- 15.2. Power Analysis: In Aim 1, hypothesis 1 our proposed sample size after accounting for expected attrition will give us 80% power to detect an effect size of at least $\eta^2=0.18$ for differences in SMA activation between active TMS and sham. For Aim 2, our proposed sample size will give us 80% power to detect an effect size of at least d = 0.90 for a within-subject improvement in tic suppression ability. Our preliminary data showed effect sizes of this magnitude.

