PROTOCOL TITLE: Transcranial Magnetic Stimulation to Augment Behavior Therapy for Tics VERSION DATE: 2/24/2022

- 15.3. Data Integrity:
 - [name] and [name], the study biostatistician, will directly train the study staff in issues of maintaining data integrity. [name] will oversee data quality control measures and design a customized randomization procedure and data management system for this project. This study will utilize the secure, web-based Research Electronic Data Capture (REDCap) system for data input. Data checking procedures will be implemented to ensure data integrity. Data file archival and back-up will be performed on a regular basis

16. Health Information and Privacy Compliance

- *16.1.* Select which of the following is applicable to your research:
 - \Box My research does not require access to individual health information.
 - I am requesting that all research participants sign a HIPCO approved HIPAA Disclosure Authorization to participate in the research (either the standalone form or the combined consent and HIPAA Authorization).
 - □ I am requesting the IRB to approve a Waiver or an alteration of research participant authorization to participate in the research.

Appropriate Use for Research:

- *16.2.* Identify the source of Private Health Information you will be using for your research (Check all that apply)
 - □ I will use the Informatics Consulting Services (ICS) available through CTSI (also referred to as the University's Information Exchange (IE) or data shelter) to pull records for me
 - I will collect information directly from research participants.
 - □ I will use University services to access and retrieve records from the Bone Marrow Transplant (BMPT) database, also known as the HSCT (Hematopoietic Stem Cell Transplant) database.
 - \Box I will pull records directly from EPIC.
 - □ I will retrieve record directly from axiUm / MiPACS
 - \Box I will receive data from the Center for Medicare/Medicaid Services
 - \Box I will receive a limited data set from another institution
 - ☑ Other. Describe: Medical record documents deemed necessary to determine inclusion criteria are met will be collected. Adult

PROTOCOL TITLE: Transcranial Magnetic Stimulation to Augment Behavior Therapy for Tics VERSION DATE: 2/24/2022

participants or parents will provide these documents themselves or complete a release of information for us to request the documents directly from their provider.

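### Aim 2, and the Aim 3 comparison of TST change, name no baseline covariate although randomisation is stratified on baseline TST and medication; pre-specifying ANCOVA gains precision at ordinary pre-post correlations for 2 degrees of freedom

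*Combined protocol and SAP*

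**What the plan says.** Section 3.1 lists within-subject change in tic suppression ability on the TST as a primary endpoint. Section 5.2 (Randomization) states: "Randomization will be stratified on baseline TST performance (tic suppressibility below or above 50%) and medication status (on vs. off".

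Section 15.1, Aim 2, uses an ANOVA to look for "differences in how the 1Hz, cTBS, and sham conditions affect change in tic suppression ability from pre- to post-treatment", and adds: "Group indicators for these conditions will be the primary predictors for the model". It names no baseline TST, medication or stratum term. Aim 3 compares the same change between 1 Hz and cTBS by ANOVA, again without covariates.

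Two other passages in 15.1 bear on this. The Aim 1 model does name its baseline value: "The predictors of the LME will include the baseline activation, group indicators for" the stimulation groups, plus baseline-by-group terms. The missing-data paragraph allows the team to "adjust models based on significant predictors of dropout", which is the only stated adjustment that could reach Aim 2.

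No allocation ratio, block size or other balancing method is given. Section 15.3 says only that a member of the study team will "design a customized randomization procedure and data management system for this project".

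**The concern.** Stratifying on a variable signals that it is expected to matter for the outcome. An analysis of change with group terms only then makes no use of it. Change scores usually correlate negatively with their baseline, so part of the residual variance is predictable from data held before randomisation.

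If allocation is also balanced within strata, the arms differ less by chance than the ANOVA standard error assumes. The test then rejects less often than its nominal level.

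This is a three-arm trial of 60, about 20 per arm if allocation is equal, so precision on a primary endpoint is scarce. Naming no covariates also leaves the choice of model open until data are seen, while the dropout rule would choose covariates by significance.

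**Working it through.** **The plan's own figure.** Section 15.2 says "our proposed sample size will give us 80% power to detect an effect size of at least d = 0.90" and calls the effect within-subject. With 20 per arm and a two-sided 5% level, one active arm against sham has noncentrality 0.9 × √(20/2) = 2.85. Power is 79.2% on 38 df, or 79.9% using the three-arm error df of 57. A paired test within one arm of 20 gives 96.8%. The stated 80% therefore matches a between-arm comparison with no attrition. Below, 0.9 is used as an assumed active-sham difference in SDs of change.

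**Inputs.** From the documents: N = 60, three arms, the two stratification factors, d = 0.90. Assumed: 1:1:1 allocation, 48 analysed (16 per arm; also 60), 5% two-sided, pre-post correlation ρ = 0.3/0.5/0.7, equal pre and post SDs, even strata.

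**Variance ratio.** With common SD σ, change has variance 2σ²(1−ρ). After regression on baseline the residual variance is σ²(1−ρ²). The ratio is (1+ρ)/2 = 0.65/0.75/0.85, with square roots 0.81/0.87/0.92. Intervals therefore narrow by about 19/13/8% in large samples.

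**Finite-sample cost.** Without stratified balance, chance imbalance in q = 2 covariates inflates the variance by about 1 + q/(N−k−q−1), where k = 3 is the number of arms. With N = 48 this is 1 + 2/42 = 1.048. Narrowing becomes 1 − √(0.65 × 1.048), and so on, or about 17/11/6%. Simulation gives 17.4/11.3/5.5% without balance and 18.9/12.7/7.0% with it.

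**Omnibus power, 16 per arm, means 0/0.9/0.9.** Noncentrality is 16 × (0.36 + 0.09 + 0.09) = 8.64 on 2 and 45 df, giving 72.2%. Dividing 8.64 by the variance ratio, on 2 and 43 df, gives 89.3/84.3/79.3%. This formula omits chance imbalance, so simulation is the better guide. The simulation used blocks of 6 within four strata, random loss, no medication effect and 6,000 trials per setting:

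| Setting (ρ = 0.3/0.5/0.7) | ANOVA power, % | ANCOVA power, % | ANOVA type I error, % |
|---|---|---|---|
| 48 analysed, balanced strata | 72/73/73 | 88/83/78 | 2.6/3.3/4.1 |
| 60 analysed, balanced strata | 84/84/83 | 95/92/88 | 2.2/2.8/3.6 |
| 48, no stratified balance | 71/72/72 | 87/83/77 | 5.1/4.7/4.9 |
| 48, stratifying score correlates 0.5 with analysed score | 71/72/72 | 87/83/78 | 4.8/4.6/5.0 |
| 48, post SD 0.8 × pre SD | 73/73/73 | 95/92/90 | not tabulated |
| 48, post SD 1.25 × pre SD | 73/71/72 | 82/76/72 | not tabulated |

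In the first row, ANCOVA type I error is 4.8/4.8/5.0%. Pooled active versus sham rises from 84/83/83% to 94/91/87%.

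**Where the gain ends.** Without stratified balance, break-even needs (1+ρ)/2 × 1.048 = 1, so ρ is about 0.91. Simulation agrees: 72.8 vs 73.0% at 0.9, 72.5 vs 71.6% at 0.95 and 72.0 vs 70.0% at 0.98. With stratified balance it gives 72.0 vs 73.2% at 0.9 and 71.7 vs 71.7% at 0.98.

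If the post SD is c times the pre SD, the variance saved is (1−cρ)²σ², with σ the pre SD. At c = 1.25 and ρ = 0.7 this is 0.0156σ² out of 0.8125σ², about 2%. Finite-sample costs absorb that.

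**The case against.** The strongest reply is that nothing here is an error. Calling the group indicators primary leaves room for other terms. The unadjusted comparison is unbiased, and its type I error is at or below nominal in the settings checked. The size of the gain rests on a correlation, an SD ratio, an attrition rate and an allocation scheme that the documents do not give. All of that stands, and it makes this an efficiency and pre-specification point.

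Four stronger readings are tempting and are not supported:

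- *The plan excludes covariates, or the result would be biased.* The text does neither. It fails to say which model will be run.
- *The ANOVA will be conservative.* That needs balance within strata and a stratifying score closely related to the outcome. The documents state neither, and without them type I error is about 5%.
- *Adjustment can never lose.* A calculation that charges only the lost degrees of freedom suggests this, but it ignores chance covariate imbalance. At ρ = 0.98 without stratified balance the loss is about 2 points.
- *Scores pile up at their limits, so the gain is larger.* Section 2.1 reports that one fifth of youth "can suppress tics to near-zero levels, and another 20% show no detectable tic decrease or even tic worsening when attempting suppression". That describes suppression under immediate reward, whereas this trial's TST has only free-to-tic and instructed-suppression conditions. Worsening is also not a floor at which scores accumulate.

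**Conclusion.** The point holds as a worthwhile, nearly costless improvement to Aim 2 and to the TST comparison in Aim 3. Under the stated assumptions with 48 analysed, ANCOVA raises omnibus power by roughly 5 to 16 points over correlations of 0.7 down to 0.3. The power gain does not need stratified balance, nor does it depend on how the 80% in Section 15.2 was derived. Only the claim of conservatism needs balance.

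The direction is secure at ordinary correlations with similar pre and post SDs. The size is not, because neither quantity is documented. It should be changed, but the planned analysis remains valid without it.

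**What to change.** In Section 15.1, pre-specify the Aim 2 primary analysis as ANCOVA of post-treatment TST (or change, which gives the same treatment estimate once baseline is in the model). The terms are treatment group, the continuous baseline value of the same tic-suppression score and medication status. Name the active-versus-sham contrasts. Use the same model for the Aim 3 comparison of TST change. Define the tic suppression ability score, whose formula is not given, so that the baseline covariate and the outcome are demonstrably the same measure. State the allocation ratio and how balance within strata is achieved.

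The cost is wording and 2 degrees of freedom. Both covariates are already needed for randomisation, so no new data, visits or participants are required. Adding the 50% stratum alongside continuous TST would use a third degree of freedom and is not needed.

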Academy of Neurology to be the first-line intervention for tics.⁶ Immediately prior to each CBIT session, participants will undergo TMS targeting the SMA. The specific type of TMS procedure will be randomly assigned between subjects and be either: 1 Hz repetitive TMS (rTMS), continuous theta burst stimulation (cTBS), or sham stimulation.

4.2. Drug/Device Handling:

TMS device. Stimulation will be delivered using a Magstim Super Rapid2 stimulator (Magstim Company Ltd, UK). The device will be used to deliver electromagnetic stimulation through a small coil positioned over a targeted area on the scalp. The manufacturer's indication for use is to stimulate peripheral nerves and the human cortex for diagnostic and research purposes.

We will use a Magstim air-cooled 70mm figure-eight coil for motor threshold determination and active TMS conditions. Sham stimulation will use the Magstim sham air-cooled coil, which produces auditory signals identical to an active coil but contains a mu-metal shield that diverts the majority of the magnetic flux such that a minimal (<3%) magnetic field is delivered to the cortex.

The device is installed and set-up at the University of Minnesota Non-Invasive Neuromodulation Laboratory (NINL). The device will only be able to be administered by trained personnel. The device is located in a locked, access controlled room.

[figure not shown]
Operation of the TMS device (MAGSTIM Super Rapid 2) will follow the procedures outlined in the attached "Operating Manual."

- 4.3. Biosafety: N/A
- 4.4. Stem Cells: N/A
- 4.5. Fetal Tissue: N/A

5. Procedures Involved

5.1. **Study Design**: The study is a double-blinded randomized control trial that will examine whether combining Comprehensive Behavioral Intervention for Tics (CBIT) with inhibition of the

PROTOCOL TITLE: Transcranial Magnetic Stimulation to Augment Behavior Therapy for Tics VERSION DATE: 2/24/2022

supplementary motor area (SMA) using transcranial magnetic stimulation (TMS) normalizes activity in the SMA-connected circuits, improves tic suppression ability, and enhances CBIT outcomes in young people with tic disorder. We will compare two rTMS procedures, 1 Hz rTMS and continuous theta burst stimulation (cTBS), against sham stimulation. Youth with chronic tics (n = 60) will complete 10 daily sessions of CBIT plus randomly assigned TMS procedure, with fMRI, behavioral, and clinical assessments before and after treatment and at 1 and 3 month follow-ups (figure 1).

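### For SMA activation, the Aim 3 comparison of 1 Hz with cTBS names no baseline term although Aim 1 adjusts for baseline, so as written it gives up precision and can differ by chance from the Aim 1 model

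*Combined protocol and SAP*

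**What the plan says.** Section 5.1 plans 60 participants: "Youth with chronic tics (n = 60) will complete 10 daily sessions of CBIT plus randomly assigned TMS procedure". Section 4.1 lists the three arms: "1 Hz repetitive TMS (rTMS), continuous theta burst stimulation (cTBS), or sham stimulation". The allocation ratio is not stated.

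Section 15.1, Aim 1, analyses SMA activation during finger tapping with a linear mixed effects (LME) model. On its terms the plan says: "The predictors of the LME will include the baseline activation, group indicators for" "the stimulation groups, and baseline x group interactions". It adds: "Random effects will be used to model within-subject variation from the first-level analyses". The stated purpose is to model "how the within-subject change in activation from pre-treatment to post-treatment differs across active and sham conditions". Sham and both active arms are therefore in one model.

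Section 15.1, Aim 3, says that changes in the Aim 1 brain target and the Aim 2 behaviour target "will be compared between active TMS groups (1Hz rTMS vs. cTBS) using ANOVA". It names no baseline term and no interaction, and it does not point back to the Aim 1 model as the source of the contrast. The plan does not say which result governs if this comparison and the 1 Hz versus cTBS contrast available from Aim 1 differ.

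**The concern.** The scans analysed in Aim 3 are those analysed in Aim 1, and the pre-treatment scan is already a covariate there. On a plain reading, Aim 3 drops that covariate and compares mean change in two arms of at most about 20 participants each. Two things are at stake.

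- **Precision.** Unless the pre/post correlation is very high, a change score carries baseline noise that adjustment would remove.
- **Consistency.** The Aim 1 model can also yield a 1 Hz minus cTBS contrast. Two unranked analyses of one set of scans can then fall on opposite sides of 0.05, which leaves room for a choice after the fact.

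**Working it through.** **Inputs.**
- From the plan: N = 60, three arms, 80% power at eta-squared 0.18 for SMA activation (section 15.2).
- Assumed: equal allocation; two-sided alpha 0.05; equal pre- and post-treatment SD; rho (the pre/post correlation) from 0.3 to 0.9; true regimen differences of 0, 0.3 and 0.9 post-treatment SD.
- The 0.9 SD difference is illustrative. The d = 0.90 in section 15.2 concerns within-subject improvement in tic suppression, not a difference between two active regimens.

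**1. The plan's own figure.** Take a three-group F test with noncentrality N × 0.18/0.82. Power is 0.896 at N = 60, 0.809 at N = 48 and 0.800 at N = 47. The stated 80% therefore fits about 47 to 48 completers if a three-group test is meant. The attrition rate is not given; 20% leaves 60 × 0.8 = 48, or 16 per arm. The plan states no power for Aim 3.

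**2. Variance of the 1 Hz minus cTBS contrast**, n per arm, SD = 1:
- change score: (2/n) × 2(1 − rho)
- baseline-adjusted, at the mean baseline: (2/n) × (1 − rho²)
- ratio: 2(1 − rho)/(1 − rho²) = 2/(1 + rho)

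Example at n = 16, rho = 0.5: 0.125 × 1 = 0.125 against 0.125 × 0.75 = 0.094, ratio 1.33.

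| rho | Variance ratio | SE ratio |
|---|---|---|
| 0.3 | 1.54 | 1.24 |
| 0.5 | 1.33 | 1.15 |
| 0.7 | 1.18 | 1.08 |
| 0.9 | 1.05 | 1.03 |

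These are large-sample values. Simulating 16 per arm with centred baseline and the baseline-by-group terms gave variance ratios of about 1.46, 1.26, 1.13 and 1.00. Arm-specific slopes therefore use up a little of the gain, and at rho 0.9 nothing is left.

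**3. Power and agreement**, 16 per arm, two-arm ANOVA of change against the three-arm interaction model (simulated):

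| True difference | rho | ANOVA of change | Adjusted contrast | Disagree on p < 0.05 |
|---|---|---|---|---|
| 0.9 SD | 0.3 | 55% | 72% | about 25% |
| 0.9 SD | 0.5 | 69% | 79% | 16–19% |
| 0.9 SD | 0.7 | 89% | 92% | 6–7% |
| 0.3 SD | 0.3 | 11% | 13% | about 11% |
| 0.3 SD | 0.5 | 13% | 15% | about 11% |
| 0.3 SD | 0.7 | 19% | 21% | about 10% |
| 0 | 0.3–0.7 | about 5% | about 5% | 3–6% |

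The 69% is the exact noncentral-t value: at rho 0.5 the change score has SD 1, so d = 0.9, and 16 per arm gives 0.693. Simulation runs gave 67% to 70%.

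**4. Source of the loss.** At n = 16 and rho 0.5, the difference detectable with 80% power is 1.024 SD for the two-arm ANOVA of change. Adding sham to the error term alone brings it to 1.012, about 1%. Adding baseline as well brings it to 0.877. Nearly all the loss comes from omitting baseline.

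**5. Where the contrast is evaluated.** With baseline-by-group terms and an uncentred baseline, the group coefficient is the effect at zero baseline. Relative to the change score, its variance is (1 + rho)/2 × (1 + m²), where m is the baseline mean divided by its SD. It is less precise than the change score once m exceeds √(2/(1 + rho) − 1): 0.73, 0.58 and 0.42 at rho 0.3, 0.5 and 0.7. The gain in steps 2 and 3 needs the contrast to be taken at the mean baseline, which Aim 1 does not specify.

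**The case against.** The strongest reply is that Aim 3 is under-specified, not wrong. It does not exclude a covariate, it refers to Aim 1 in parentheses, and the plan uses the term ANOVA loosely: Aim 1 expresses its effect size in ANOVA terms for an endpoint that it analyses by LME. This stands in part. If adjustment is intended, one sentence settles the matter. As the text reads now, an analyst would be entitled to run the unadjusted comparison.

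Some stronger readings are tempting, and the documents do not support them.

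- **Bias, or two different treatment effects.** A reader might infer that the effect is defined in two ways. Under randomisation, the difference in mean change and the adjusted contrast at mean baseline target the same average difference, and both hold type I error near 5%.
- **The regimen choice depends on it.** The only selection rule in section 15.1 applies when both regimens beat sham, and it uses t-tests on safety and feasibility. No decision is tied to the neural ANOVA. Nor does Aim 1, framed as active versus sham, say that it will report a 1 Hz versus cTBS contrast.
- **Leaving out sham is costly.** It accounts for about 1% of the detectable difference.
- **The same mismatch holds for connectivity.** Aim 1 writes out no baseline-adjusted model for SMA-DLS or SMA-M1, so there is nothing for Aim 3 to contradict there.

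It is also fair to say that 0.9 SD between two active regimens is generous. Section 5.2 describes theta burst and conventional rTMS as comparable in their effect on cortical excitability.

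**Conclusion.** The point holds as an avoidable loss of precision and an unranked pair of analyses, documented for SMA activation only. Its size depends on a correlation that the plan does not give: moderate at rho 0.3 to 0.5, small at 0.7, negligible at 0.9. Adjustment adds about 17, 10 and 3 percentage points of power at rho 0.3, 0.5 and 0.7 if the regimens truly differ by 0.9 SD. At 0.3 SD it adds about 2 points, and neither analysis would be informative at those correlations. Chance disagreement on significance runs from 3–6% of trials with no true difference to about 25% at 0.9 SD and rho 0.3. All this assumes equal allocation, 16 completers per arm, normal data and a contrast taken at the mean baseline. The change is worth making because the baseline scan is already collected and modelled.

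**What to change.** In section 15.1, Aim 3:

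- **SMA activation.** Replace the ANOVA of change with the 1 Hz minus cTBS contrast and its confidence interval from the three-arm Aim 1 model. State that baseline activation is centred, so that the contrast is evaluated at the overall mean baseline. The three pairwise effects then agree by construction.
- **SMA-DLS and SMA-M1 connectivity.** Add the participant's baseline connectivity value as a covariate in the Aim 3 comparison.

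This costs a sentence or two in the plan and no extra data or participants. The price is reliance on a common error variance across the three arms and a few degrees of freedom for the slope terms.
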